Engaging Medically Complex Veterans in Tele-Rehabilitation Using a Biobehavioral Approach: A Pilot Study of Feasibility and Acceptability

NCT04942613

July 14, 2022

COMIRB Protocol

COLORADO MULTIPLE INSTITUTIONAL REVIEW BOARD
[name] [contact] [contact]

Protocol #: 21-2773

Project Title: Engaging Medically Complex Veterans in Tele-Rehabilitation Using a Biobehavioral Approach: A Pilot Study of Feasibility and Acceptability

Principal Investigator: [name] [name]

Version Date: 07.14.2022

I. Hypotheses and Specific Aims:

This is a single-site, randomized pilot study using a two-group (GROUP1 and GROUP2) crossover design. Fifty Veterans with medical complexity and deficits in physical function will participate. Outcomes will be assessed at baseline (pre-intervention), 6 weeks (intervention mid-point), 12 weeks (end of intervention), and 24 weeks.

AIM 1: To determine the feasibility and acceptability of a multicomponent telerehabilitation program.

Hypothesis 1a: 75% of Veterans will achieve $\geq 80\%$ adherence as measured by attendance.

Hypothesis 1b: At least 75% of Veterans will perceive the program as acceptable ($\geq 4/5$ on Acceptability of Intervention Measure¹³) and feasible ($\geq 4/5$ on Feasibility of Intervention Measure). In addition, we will monitor adverse events and categorize severity (mild, moderate, severe) and relatedness (definitely, probably, possibly).

AIM 2: To assess the preliminary response of a multicomponent telerehabilitation using a two-group randomized crossover design and determine variability estimates. Outcomes for this aim are accelerometer-based physical activity, physical function, quality of life, and loneliness.

Hypothesis 2: At program end (GROUP1 12 weeks, GROUP2 24 weeks), participants will have a trend of improved outcomes (accelerometer 7-day average step count with ActiGraph physical activity monitors (ActiGraph Inc. Pensacola FL, primary) compared to program start (GROUP1 baseline, GROUP2 12 weeks). In addition, using the pooled intervention sample, variability estimates (standard deviation), will be determined for change in physical activity, physical function (,30 second sit to stand¹⁴) and self-report measures of physical function (Activity Measure for Post-Acute Care¹⁵), quality of life (PROMIS 29 Profile v2.0¹⁶), and loneliness (3-item loneliness scale¹⁷ Berkman Social Disengagement Scale¹). This will allow for sample size estimates for the subsequent larger effectiveness trial.

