We propose a pilot, two-arm randomized trial using a waitlist control to determine the feasibility, acceptability, and safety (AIM 1) of a 12-week multicomponent telerehabilitation program. We will also assess the preliminary response (AIM 2) to this 12-week intervention. Participants (n=50) will be randomized to GROUP1 or GROUP2 using computer-generated random blocks of 2 and 4, stratified by sex. A waitlist control (GROUP2) will be used to simultaneously achieve the aims and ensure that all participants receive the intervention. Data will be collected at baseline (pre-intervention),

6-weeks (intervention midpoint for GROUP1), 12 weeks (intervention end for GROUP1, primary endpoint), and 24 weeks.

Setting & Recruitment:

Following consent and prior to baseline assessment and randomization, each participant will complete a physical therapy evaluation performed by a licensed physical therapist. The purpose of this evaluation is to ensure the Veteran is appropriate for the planned intervention and is eligible for the study. The evaluation may include standard evaluation tasks including but not limited to chart review, subjective history, and functional assessment.

Initial evaluation, intervention, and testing will occur through telehealth via VA Video Connect using a site-to-home format. Dedicated telehealth rooms are available for the study team in the ECHCS GRECC. Veterans will have the option of using their personal device (e.g., tablet, computer) or a VHA-issued tablet.

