Aim 2: Preliminary responses to the interventions will be determined via performance-based and self-report measures. Physical activity behavior outcomes (hypothesis 2) will include average 7-day step count (accelerometry; primary), self-efficacy (Self-Efficacy for Exercise Scale²) and exercise readiness to change (Exercise Stages of Change).⁷⁰ Physical function outcomes will include 30 second sit to stand test,³ arm curl test,⁷² 2-minute step test,⁷² and self-report Activity Measure for Post-Acute Care (AM-PAC).¹⁵ Social isolation and loneliness outcomes will include 3-Item Loneliness Scale¹⁷ and the Berkman Social Disengagement Scale.¹ The PROMIS-29 v2.0¹⁶ will measure quality of life (summative score), social support (subscale), and mental health (subscale). In addition, descriptive measures will be collected at baseline including demographics, medications, cognition (T-MoCA⁶⁹), depression (Patient Health Questionnaire-9 for depression⁷³), anxiety (General Anxiety Disorder-7⁷⁴), Mobile Device Proficiency Questionnaire-16,⁷⁵ and comorbidities (Functional Comorbidity Index⁶⁸).

ActiGraph physical activity monitors (ActiGraph Inc. Pensacola FL) will be used to obtain an objective measure of physical activity (PA). ActiGraph activity monitors assess PA using accelerometry, which allows objective evaluation of the relative volume (steps/day) and intensity (activity counts) of physical activity with high validity and reliability.⁷⁶⁻⁷⁸ Each participant will wear the ActiGraph for 10 days at the beginning and end of their intervention window (baseline and week 12 for GROUP1, week 12 and week 24 for GROUP2). The ActiGraph monitor will be used only for outcome data (not intervention) and provides no feedback to participants.

E. Description, Risks and Justification of Procedures and Data Collection Tools:

Potential Risks (Aim 1 and Aim 2)

Study Intervention and Assessments

We anticipate no greater risk than the minimal risk associated with standard telerehabilitation for Veterans participating in this study. All interventions and assessments are considered a part of physical therapy clinical practice. Because a physical therapist is not physically present with the participant during sessions, there is an increased risk for falls compared to in-person rehabilitation. Exercise is associated with inherent risks including muscle soreness, muscle strain, shortness of breath, and cardiac events. Precautions will be taken to minimize risks as follows:

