3. All study-related intervention and assessment activities will be supervised by a licensed physical therapist. Physical therapists will conduct a falls risk assessment at the first telehealth sessions to determine the participants' level of function and potential needs for support and safety during the session (e.g., use of hand-held support on a countertop during exercise); this approach will reduce the risk for falls and injury. Additionally, interventions and assessments will not be conducted for patients who are unable to perform the tasks (by patient report or clinicians' judgment).
4. Furthermore, when at all possible, sessions will be conducted when another adult is present as an additional safety measure.
5. When completing surveys with potentially sensitive questions, participants will be reminded that they can choose not to answer any question and that all data is only linked to a participant ID in order to maintain confidentiality and anonymity.

F. Potential Scientific Problems:

Mobile-Health technology: Durability and continued functionality of technology is a concern when using any technology. The mobile-health tablets used in this study have been implemented for standard-of-care use for a variety of purposes currently in the VA ECHCS. If a tablet becomes dysfunctional, replacement units are available so that an immediate back-up unit can replace the dysfunctional unit. The VHA will provide mobile-health technical support for the duration of the study. Finally, the intervention is not dependent on type of tablet used, so changes in mobile-health tablets in the future will not necessitate a change in intervention.

Lack of long-term follow-up: Creating a change in physical activity behavior for an older adult population is a major challenge. We will collect data out to 24 weeks (GROUP1) to determine maintenance of intervention effects. We expect that activity changes may be reduced at the 24-week time period for GROUP1 compared to the 12-week test point, but that the activity will continue to be higher than baseline, based on data from studies of patients with other chronic diseases.⁷⁹

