Heterogeneity of medically complex older adults: Medically complex older adults are heterogeneous in age, cognitive status, medical status, psychological comorbidity, living environment, and social support.²² Additionally, they experience acute exacerbations of chronic conditions impacting their response to treatment and contributing to high drop-out rates among this population. To accommodate for this from our experiences, we anticipated a higher attrition rate (20%) and adjusted enrollment accordingly.

G. Data Analysis Plan:

Analysis Plan. Analyses will be performed in SAS v 9.4 or above and hypothesis tests will be two-sided, assuming an alpha level of 0.05. Participant characteristics and outcome variables will be summarized using means, standard deviations (SD), medians, ranges, N and percent, as appropriate.

Aim 1. The percent of Veterans (1) achieving $\geq 80\%$ adherence and (2) scoring $\geq 4/5$ on the Acceptability of Intervention Measure will be calculated with associated 95% exact binomial confidence intervals. We will additionally calculate the proportion of adverse events that are found to be possibly, probably, or definitely related to the intervention.

Aim 2. Given the small samples, the median change from baseline to 12 weeks for those randomized to the intervention will be compared between the groups using a Wilcoxon rank-sum test for each outcome of interest (7-day average step count as primary). Estimates of variability (SD) in the change from pre to post-intervention for the pooled sample completing the intervention (N=40) will be calculated for each outcome and reported with 95% CIs. These estimates and the CIs will inform sample size calculations for a future effectiveness trial.

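### Under the ActiGraph wear schedule the waitlist group has no baseline step count, so the planned between-group test of step-count change cannot be run and GROUP1 step maintenance cannot be checked

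*Combined protocol and SAP*

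**What the plan says.** All references are to the combined protocol and SAP.

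- **Wear schedule (section D, Outcomes, Aim 2).** Every participant has two 10-day ActiGraph wear periods, one at the start and one at the "end of their intervention window (baseline and week 12 for GROUP1, week 12 and week 24 for GROUP2"). No other text sets wear times.
- **Planned test (section G, Aim 2).** The planned analysis is stated as "median change from baseline to 12 weeks for those randomized to the intervention will be compared between the groups using a Wilcoxon rank-sum test"; this applies to every outcome, with 7-day average step count named as primary. Tests are two-sided at 0.05.
- **Pooled variability (section G, Aim 2).** "Estimates of variability (SD) in the change from pre to post-intervention for the pooled sample completing the intervention (N=40") are to be reported with 95% CIs.
- **Hypothesis 2 (section I).** Outcomes at program end are "compared to program start (GROUP1 baseline, GROUP2 12 weeks"). This is a within-person contrast.
- **Maintenance (section F, long-term follow-up).** "We will collect data out to 24 weeks (GROUP1) to determine maintenance of intervention effects", and then "We expect that activity changes may be reduced at the 24-week time period for GROUP1 compared to the 12-week test point".
- **General schedules.** Section I: "Outcomes will be assessed at baseline (pre-intervention), 6 weeks (intervention mid-point), 12 weeks (end of intervention), and 24 weeks". Section D likewise lists "12 weeks (intervention end for GROUP1, primary endpoint), and 24 weeks". Neither is split by group for outcome visits, and neither mentions the monitor.

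**The concern.** A rank-sum test of change needs a change score in both groups. The wear schedule follows each participant's own treatment window. That suits the within-person contrast of Hypothesis 2, but it leaves the waitlist period, which is the randomised control period, with no starting step count. The section G test and the section D wear schedule cannot both stand for step count.

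The general schedules would fill the gap if they governed step count, but they are not device-specific and the documents do not rank them. Staff who follow the specific instruction would not issue monitors to GROUP2 at baseline, and a missed baseline wear cannot be recovered. The analyst would then have to choose a replacement comparison after the data are in, among options with different estimands.

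The section G sentence is also unclear in itself: it refers to change in those randomised to the intervention, yet compares it between groups.

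**Working it through.** **Inputs.** 50 randomised, 25 per group, with 40 expected to complete (inclusion/exclusion section); wear visits (section D); analyses (sections F, G and I). Equal completion by group is an assumption.

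**The plan's own figure.** 40 / (1 − 0.20) = 50 randomised, which reproduces the stated number. The plan gives no power calculation to reproduce.

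**Visits needed against visits with wear.** GROUP1 wears at weeks 0 and 12; GROUP2 at weeks 12 and 24.

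| Analysis | GROUP1 needs | GROUP2 needs | Missing | Result |
|---|---|---|---|---|
| Between-group change, 0–12 | 0, 12 | 0, 12 | GROUP2 week 0 | about 20 v 0; test undefined |
| Pooled pre/post change | 0, 12 | 12, 24 | none | N = 40; estimable |
| GROUP1 maintenance, 12–24 | 12, 24 | – | GROUP1 week 24 | 0 step counts |
| Week-12 level between groups | 12 | 12 | none | about 20 v 20; estimable |

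**What the week-12 fallback costs in precision.** Assume a common SD *s* at both visits, correlation *r* between them, and *n* per group.

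- Difference in week-12 means: variance = 2s²/n.
- Difference in mean change: variance = 2 × 2s²(1 − r)/n = 4s²(1 − r)/n.
- Ratio, week-12 level to change = 1 / [2(1 − r)].
- Equivalent size of a change-score comparison, starting from 20 per group = 20 / ratio = 40(1 − r).

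| r (assumed) | Variance ratio | Equivalent n per group |
|---|---|---|
| 0.3 | 1/1.4 = 0.71 | 28 |
| 0.5 | 1/1.0 = 1.00 | 20 |
| 0.7 | 1/0.6 = 1.67 | 12 |
| 0.8 | 1/0.4 = 2.50 | 8 |

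Simulation with 20 per group and 40,000 runs gave 1.00, 1.67 and 2.49 at r = 0.5, 0.7 and 0.8. The documents give no *r*. These ratios are for means and are only a guide to the rank-sum test.

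**Wear periods.** Now 2 × 50 = 100. Adding GROUP2 baseline: 100 + 25 = 125. Adding GROUP1 week 24 as well: 125 + 25 = 150.

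**The case against.** The strongest reply is that this is an inconsistency and not proof that data will be missing. The wear sentence does not forbid other wear, and the general schedules, read literally, supply both missing wear periods. That is correct, and it is why the finding is conditional on the device-specific schedule. It does not remove the problem: if the general schedules are meant to govern, the wear sentence is wrong and still needs amending.

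Second, no sentence calls the rank-sum test the primary analysis of Aim 2. Step count is the primary outcome, Hypothesis 2 is a within-person contrast that expects only a trend, and this is a pilot. This stands as a limit on scope. Even so, the test is the only hypothesis test that section G specifies for Aim 2, its named lead outcome is step count, and section D calls 12 weeks the primary endpoint.

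Third, the simplest edit would be to exempt step count from the test. That would give up the only randomised step-count comparison, although a week-12 comparison is available without added wear.

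Fourth, section G plans no maintenance analysis, so none is lost. This is also correct; what lacks support is the statement about GROUP1 activity in section F.

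Fifth, section G's general sentence on summarising outcomes by means and medians may cover the pre/post change. It may, but it does not name the change or give it a confidence interval.

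Last, below r = 0.5 the unadjusted change score is less precise than the week-12 comparison. That is true and is shown in the table. An added baseline is therefore not a guaranteed gain in precision for an unadjusted change score; what it restores is the planned estimand.

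**Conclusion.** The concern holds. Under the only schedule that sets monitor wear, the between-group test of baseline-to-12-week step change has about 20 GROUP1 values and no GROUP2 values, and GROUP1 has no step counts at 24 weeks. The figure of 20 assumes the planned 20% attrition falls equally on both groups; the zeros do not depend on it.

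The damage is limited to the step-count change comparison and step-based maintenance in GROUP1. Aim 1, the pooled pre/post SD, the Hypothesis 2 contrast, the non-accelerometer outcomes, the follow-up interviews and a randomised week-12 step comparison all remain available. The fallback's precision relative to the planned change score depends on an unknown correlation: it is better below r = 0.5 and worse above it.

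This must be settled before data collection, because a missed baseline wear cannot be recovered.

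**What to change.** **Preferred.**

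- Amend the wear schedule in section D so that both groups wear the ActiGraph for 10 days at baseline (completed before randomisation), week 12 and week 24.
- Reword section G so that change from baseline to 12 weeks is compared between GROUP1 and GROUP2.

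**If the added wear is refused.**

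- Change section G so that the primary step-count analysis is a between-group rank-sum comparison of week-12 steps.
- Limit the maintenance statement in section F to outcomes that are measured in GROUP1 at 24 weeks.

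**Under either route.**

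- State that GROUP2's week-12 wear ends before its first program session. The current text places that wear only at the beginning of the intervention window, so treated days could enter the control value.
- Add to section G the pooled pre/post median step change with a 95% CI for Hypothesis 2, labelled as uncontrolled.
- State in sections I and D which visits include the monitor.

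**Cost.** A protocol amendment. The section G test alone needs 25 more wear periods (100 to 125). Step-based maintenance needs a further 25 (150 in total at full retention), which makes one extra 10-day wear per participant. Completing baseline wear first can delay randomisation by about 10 days. The fallback adds no wear, but it changes the estimand from change to week-12 level and loses precision if r exceeds 0.5.

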Based Primary Care, and inpatient and outpatient rehabilitation settings. Potential Veterans with whom we have a treatment relationship will be pre-screened through standardized chart review followed by standardized phone screen. If eligible and interested in participating, Veterans will provide informed consent and be enrolled in the study; once enrolled, they will be randomized to either a waitlist control (GROUP2) or experimental (GROUP1) group. Participants will complete surveys and direct observation (Aims 1 & 2). Veterans will also undergo performance-based assessments of physical activity and physical function and complete self-reported measures for physical function, quality of life, loneliness, social support, and mental health.

Formal Inclusion/Exclusion Criteria

Inclusion

- ≥ 60 years of age
- Multiple chronic conditions (Functional Comorbidity Index⁶⁸ ≥ 3)
- Impaired physical function (≤ 10 on 30 second sit to stand)

Exclusion

- Life expectancy < 12 months
- Acute or progressive neurological disorder (e.g., Amyotrophic Lateral Sclerosis, recent stroke)
- Moderate to severe dementia without caregiver assistance (< 18 on telephone Montreal Cognitive Assessment (T-MoCA)⁶⁹)
- Unstable medical condition precluding safe participation in progressive rehabilitation (e.g., unstable angina) as defined by ACSM guidelines

We plan to randomize 50 Veterans (25 randomized to each group), with the goal of having 40 Veterans complete the study (20% attrition rate). Due to our enrollment process, we plan to have 70 Veterans sign the informed consent; this will allow for up to 20 Veterans to complete evaluation but be found ineligible based on identified exclusion criteria. The goal of the study is to obtain a representative sample of older Veterans at risk for, or presenting with, impaired physical function contributing to fall risk, physical dependence, and risk for hospitalization. Both sexes and all races are included in the study, however the Veteran population is predominantly male and Caucasian, which will be reflected in the enrollment.

D. Study Design and Research Methods

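### Drop-out is expected to be related to response, but Aim 2 sets no missing-data rule, limits the change SD to completers and models no 6-week data

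*Combined protocol and SAP*

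**What the plan says.** Section F (Potential Scientific Problems, paragraph on heterogeneity) gives one cause for both outcome and loss: "they experience acute exacerbations of chronic conditions impacting their response to treatment and contributing to high drop-out rates among this population". The response follows at once: "we anticipated a higher attrition rate (20%) and adjusted enrollment accordingly". The sample-size paragraph after the eligibility criteria carries this through: "We plan to randomize 50 Veterans (25 randomized to each group), with the goal of having 40 Veterans complete the study (20% attrition rate").

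Section G (Data Analysis Plan, Aim 2) contains two analyses.

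- **Between groups.** Change from baseline to 12 weeks "will be compared between the groups using a Wilcoxon rank-sum test for each outcome of interest (7-day average step count as primary"). No analysis set is named.
- **Variability.** The SD of the pre-to-post change is estimated in the "pooled sample completing the intervention (N=40") and reported with 95% CIs, to size a later effectiveness trial.

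Section I lists an assessment at "6 weeks (intervention mid-point"), and Section D describes that visit as the midpoint for GROUP1. No Aim 2 analysis uses it, beyond whatever the general descriptive summaries in Section G may cover. The ActiGraph paragraph in Section D places monitor wear at baseline and week 12 for GROUP1 and at weeks 12 and 24 for GROUP2. Neither document part states an intention-to-treat set, a missing-data method or a sensitivity analysis.

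**The concern.** When one event both worsens response and causes loss, the people without an outcome are not a random fifth of the sample. Enlarging enrolment restores the number of completers but not the kind of Veteran who left.

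Three results are exposed. The within-person change behind Hypothesis 2 has no control arm to cancel the selection, so it can look too favourable. The SD, which is the pilot's stated product for planning the next trial, can be too small if the poorest changes are missing. The between-group test can be distorted if loss differs between arms. That is plausible, because one arm is offered 36 exercise sessions (12 individual and 24 group) and the other 6 educational sessions over the same 12 weeks.

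There is also a second route to missing values. The safety procedures in Section E say that assessments are not done when a Veteran cannot perform the tasks, so a Veteran who is retained but doing badly may also lack a performance score.

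**Working it through.** **1. The plan's own figure.** 40 / (1 − 0.20) = 50 randomised, and 50 × 0.80 = 40. The 70 consents less up to 20 ineligible also give 50. The enrolment arithmetic is right. No effect size, SD or power is stated, so everything below is a range under assumptions.

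**2. Within-person change.** Let d = 0.20 be the share lost and let drop-outs' true mean change lie D completer SDs below that of completers. The completer mean is then too high by d × D. If the two sets have the same within-set SD, the variance in all randomised relative to completers is 1 + d(1 − d)D². That ratio is also the factor by which a future N would be too small.

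| D (assumed) | Overstatement, SD | Future N factor |
|---|---|---|
| 0 | 0 | 1.00 |
| 0.25 | 0.05 | 1.01 |
| 0.5 | 0.10 | 1.04 |
| 1.0 | 0.20 | 1.16 |
| 1.5 | 0.30 | 1.36 |

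Example for D = 1: 0.20 × 1 = 0.20, and 1 + 0.20 × 0.80 × 1 = 1.16. In the extreme case, where exactly the lowest 20% of a normal distribution is lost, the figures are 0.35 (in full-sample SDs) and 1.72.

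**3. What the planned CI covers.** At N = 40 the 95% CI for an SD runs from 0.82 to 1.28 times the estimate. This is sampling error only and does not allow for selection.

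**4. Between groups, by formula.** With the same D in both arms, the bias in the difference is (d₁ − d₂) × D, where 1 is the program and 2 the waitlist.

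- 20% and 20%: zero for any D.
- 30% and 10%: +0.10, +0.20 and +0.30 SD for D = 0.5, 1.0 and 1.5.
- 10% and 30%: −0.10, −0.20 and −0.30 SD.

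**5. Type I error of the rank-sum test.** This was simulated with 25 per arm, no true effect and 10,000 runs. In each arm 30% have an exacerbation that lowers change by 0.5, 1.0 or 1.5 SD, and all drop-outs come from that 30%. With 20% loss in both arms, the error was 0.045 to 0.048. With 30% lost from the program and 10% from the waitlist, it was 0.057, 0.092 and 0.130.

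**6. Value of week 6.** This was simulated with 25 per arm, about 20% loss per arm and a true effect of 0.50 SD. Correlations were assumed to be 0.7 between adjacent visits and 0.6 from baseline to week 12. The completer estimate is compared with a likelihood estimate that uses week 6.

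| Who is lost | Completers | With week 6 |
|---|---|---|
| Random loss in both arms | 0.50 | 0.50 |
| Poor week-6 change, program arm only | 0.62 | 0.50 |
| Poor week-6 change, both arms | 0.50 | 0.50 |
| Poor week-6 change, waitlist only | 0.39 | 0.50 |
| Poor unseen week-12 change, program arm only | 0.69 | 0.63 |

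The exact values move by a few hundredths with the assumed strength of selection; the pattern does not.

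**The case against.** A reader might infer that the completer analysis will flatter the program against the waitlist, by roughly a quarter (0.62 against 0.50). The documents do not support a fixed direction or size. Section F attributes exacerbations and drop-out to the population, not to one arm. Equally selective loss leaves the group comparison about unbiased, and heavier selection in the waitlist makes the program look worse. The 0.62 needs selection in the program arm alone.

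A reader might also infer that all of Aim 2 is a completers analysis. Only the SD is explicitly so. A Veteran who stops attending may still be assessed at week 12, and the rank-sum sentence does not exclude that person.

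A third inference, that the 6-week data would cure the problem, goes too far. Step count, the primary outcome, has no week-6 wear. The documents do not say which instruments are given at that visit. Anyone who leaves before it contributes nothing there, and loss driven by later events is only partly corrected (0.63 in the last row above). Nor does a baseline, week 6 and week 12 model touch the pooled SD, which also draws on GROUP2's weeks 12 to 24.

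Finally, the plan chose rank methods because the samples are small, retention will be reported, and Hypothesis 2 looks only for a trend. Replacing the rank test with a normal-theory model for every outcome, including short ordinal scales, would be a trade-off rather than a clear gain.

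All of this stands. It limits direction, size and remedy. It does not supply the missing analysis set, missing-data rule or sensitivity analysis.

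**Conclusion.** The point holds in a limited form. The plan describes drop-out related to response and answers it only with numbers. At 20% attrition the within-person change can be overstated by 0.05 to 0.30 SD and the next trial under-sized by a factor of 1.01 to 1.36, if drop-outs fare 0.25 to 1.5 SD worse. The between-group estimate can be biased either way when loss differs between arms (about 0.39 to 0.62 SD around a true 0.50, with selection on week-6 change) and is roughly unbiased when it does not.

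The drop-out deficits, unequal loss rates, 30% exacerbation share, correlations and true effect are assumptions; the documents give none of them. The SD effect is modest beside its sampling error at N = 40 for most of the range, but the planned CI will not reveal it. This is worth correcting before analysis and does not undermine the pilot.

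A linked inconsistency is independent of these assumptions. No baseline ActiGraph wear is listed for GROUP2, so the baseline-to-12-week step-count comparison in Section G cannot be formed as written.

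**What to change.** In Section G, Aim 2:

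1. Keep the Wilcoxon test and state its set: all randomised Veterans with a 12-week value, whether or not they finished the program. Seek the 12-week and 24-week assessments from those who stop attending.
2. For continuous outcomes collected at week 6, name them and add a likelihood-based repeated-measures sensitivity analysis (baseline, week 6, week 12; group by time; sex). Say that it corrects only for drop-out explained by observed values.
3. For step count, add a worst-rank sensitivity analysis in which Veterans who leave for health reasons take the lowest rank. Record and report reasons for drop-out by arm.
4. Report the change SD for everyone with pre and post values, with completers shown alongside, and state that the CI covers sampling error only.
5. Reconcile the ActiGraph schedule in Section D with the step-count comparison in Section G.

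The cost is mostly SAP wording and standard SAS procedures. Item 1 needs some follow-up effort. Item 3 needs a withdrawal-reason field, which the documents do not say exists. Item 5 may need a change to the wear schedule or to the comparison. The reported response may become less favourable and the SD larger.
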